Specific Aim3: Determine the relationship between markers of DNL, liver fat accumulation and serum concentrations of lipids, uric acid and liver function markers before and after the fructose challenge

- We will measure serum concentrations of liver function markers, lipids and uric acid at week 0 and week 3;
- As in previous aims, data will be analyzed using students T test, and Pearsons correlations.

Subject Population	Inclusion Criteria
key criteria for Inclusion and Exclusion:	
 Subjects between 12 and 40 years No history of alcohol abuse (> 7 drinks per week) History of fructose intake of < 14 drinks per week Caucasian ethnicity BMI > 25kg/m² – 32kg/m² or 85th -99th percentile but otherwise healthy
	Exclusion Criteria
	
 ages < 12 and > 40 years Pregnant/lactating known alcohol abuse or fructose intake > 14 drinks per week not of Caucasian ethnicity glucose levels > 100 mg/dl if fasting, > 140mg/dl if within 2 hours post meal and > 200 mg/dl if random sample taking anti-hypertensive, anti-diabetic, uric acid and/or lipid-lowering medications known diagnosis of diabetes, fructose intolerance, chronic kidney disease, NAFLD or any liver-related disease, hypertriglyceridemia, polycystic ovary syndrome, hypothyroidism, obstructive sleep apnea, hypopituitarism and hypogandism BMI < 25kg/m² or > 32 kg/m² or < 85th or > 99th percentile Liver fat fraction >5% as per baseline MRI scan
Number Of Subjects	200 for first phase and 48 for the second and third phases
Study Duration	The first phase will be about 30 minutes and the second and third phase will be divided into two visits. Both visits in both phases will be about 3.5 hours each.
Study Phases	(1) Screening: We will screen participants for eligibility to participate in the study based on the inclusionary/exclusionary criteria specified above. The 200 children and young adults selected to participate will provide saliva which will be used to extract DNA and then genotype 10 SNPs. These SNPs are selected based on their association with de novo lipogenesis (DNL) or liver fat accumulation in previously published studies in Caucasians. We will select 12 children and 12 young adults with more than 15 risk alleles and 12 children and 12 young adults with less than six number of risk alleles.
Screening	
Study Treatment	
Follow-Up	

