Safety Evaluations	
At screening, to check for blood glucose values, we will conduct a spot glucose check using a glucometer (Accu-Chek, Roche Diagnostics, CH) to check that the glucose levels of the participants are in the normal range (fasting < 100mg/dl, post meal < 140 mg/dl and random < 200 mg/dl). Secondly, we will have a physician who will be available if needed. We will also conduct pregnancy test if needed.
 
Also, we will exclude participants for further participation if we find that the participant has high liver fat fraction (>5%) during our baseline MRI scan¹⁰. The participant will be given a report that they can show to their physician for treatment.

Statistical And Analytic Plan	Our main outcome measure is change in liver fat via MRI scan, fatty liver index equation and through fibroscan measurements. We will also measure serum concentrations of other lipids, liver function markers and uric acid. Data will be assessed using descriptive measures and confidence intervals. Paired t-tests and repeated measures regression analysis will be performed to explore the significant differences between week 0 and week 3.
DATA AND SAFETY MONITORING PLAN	A data and safety monitoring plan will be instituted for this study that will ensure adherence to the protocol approved by UNC IRB. [name] (PI) and co-investigators will review the phenotype and genotype data as they are generated. Any adverse event that is reported to either the principal investigator or her designated research associates by the subject or medical staff caring for the subject and which meets the criteria will be documented as such. Any event that is reported will then generate an adverse event report, which will be submitted to the IRB. The report will include a description of the event, when and how it was reported, as well as any official chart records or documentation to corroborate the event or the reporting of the event

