1.3 Non-Clinical and Clinical Study Findings

There are no immediate benefits. In long-term, we can provide genetic risk-guided diet plans to individuals who may be at high risk.

Risks: We don't anticipate major risk since we will exclude individuals who are diabetic, pre-diabetic, have high liver fat at baseline and are at high risk for these and other metabolic diseases. The only risk can be weight gain. We will advise on cutting calories elsewhere in their daily diet. We will also advise the participants to avoid fruit juices and other sodas for the duration of 3 weeks.

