3.2 Allocation to Treatment Groups and Blinding (if applicable)

- We will allocate participants to high and low genetic risk groups

3.3

Study Duration, Enrollment and Number of Subjects

- The study has three phases. First phase will have 200 participants who will visit Human Research Core clinical suite and spend about 30 minutes providing saliva sample and completing a brief questionnaire.
- Second and third phases will have 48 participants. They will first undergo a MRI scan and next day a 3 hour acute fructose challenge (total time 3.5 hours) and then will consume sugar drink as given to them. They will visit again at the end of week 3 for further biomarker, MRI scan and fibroscan measurements.

3.4

Study Population

- Inclusion criteria: Caucasian children and young adults, overweight/obese, ages between 12 and 40 years and no history of alcohol abuse (> 7 drinks per week for a year) and no history of excessive fructose intake (> 14 drinks per week for a year). We will conduct a spot glucose check using a glucometer (Accu-Chek, Roche Diagnostics, CH) to check that the glucose levels of the participants are in the normal range (fasting < 100mg/dl, post meal < 140 mg/dl and random < 200 mg/dl).
- Exclusion criteria includes ages < 12 and > 40 years, healthy weight or morbidly obese, known alcohol abuse, not of Caucasian ethnicity, pregnancy, lactation, glucose levels > 100 mg/dl if fasting, > 140mg/dl if within 2 hours post meal and > 200 mg/dl if random, baseline MRI scan of liver fat fraction > 5%²⁷, and known diagnosis of diabetes, fructose intolerance and chronic kidney disease, use of lipid or uric acid lowering medications.

4

STUDY PROCEDURES (what will be done)

4.1

Screening/Baseline Visit procedures

Phase 1: Recruitment and screening of participants:

Screening: We will recruit 200 Caucasian children and young adults fulfilling our inclusionary criteria: ages between 12 and 40 years, overweight or obese, no history of fructose intake > 14 drinks per week and alcohol abuse (> 7 drinks per week for a year). Height will be measured to the nearest 0.1 cm by a stadiometer situated against the wall in an upright standing position. Height and weight recorded will be used to calculate BMI as kg/m². We will match all participants for BMI (25kg/m² -32kg/m² or 85th-99th percentile).

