We will conduct a spot glucose check using a glucometer (Accu-Chek, Roche Diagnostics, CH) to check that the glucose levels of the participants are in the normal range (fasting < 100mg/dl, post meal < 140 mg/dl and random < 200 mg/dl). The exclusion criteria includes ages < 12 and > 40 years, known alcohol abuse or fructose intake > 14 drinks per week, not of Caucasian ethnicity, glucose levels > 100 mg/dl if fasting, > 140mg/dl if within 2 hours post meal and > 200 mg/dl if random, and known diagnosis of diabetes, fructose intolerance and chronic kidney disease.

We will collect saliva from the eligible 200 children and young adults, extract DNA and genotype 10 SNPs shown in Table1.

Genotyping: SNPs will be genotyped from DNA extracted from saliva. Genotyping will be conducted in [name] lab using TaqManSNP genotyping assays (Applied Biosystems, Foster City, CA). The minor allele frequencies (MAFs) of these SNPs range between 7 and 49% based on Caucasian ethnic background. Therefore we are confident about finding 48 individuals with all 10 SNPs. If we don't find individuals with the 10 SNPs, we will mine the literature and find more SNPs that have a role in liver lipogenesis.

4.2

Intervention/Treatment procedures (by visits)

Phase2: Selection of 48 participants for the acute fructose challenge and 3-week intervention study:

The risk allele will be defined as the allele that is associated with higher levels of liver lipogenesis or fat as per previously published studies in Caucasians. The number of risk alleles will range from 0 to 20. The SNP will get a score of 2 with two risk alleles, 1 with one risk allele and 0 with no risk alleles. All the score will be added to get a cumulative score between 0 and 20 for 10 SNPs. We will select participants having > 15 risk alleles and < 6 risk alleles for our acute challenge and 3-week intervention study.

Phase 2&3- visit 1- MRI scan: The 48 individuals enrolled will visit the UNC NRI clinical suite run by the Human Research Core. After obtaining consent, they will be taken to the WakeForest Imaging center for baseline MRI scan. Studies have shown that 5-6% of liver fat is considered normal and anything more than that can reflect increased risk for fatty liver. If the MRI report of the participants shows liver fat > 6%, we will consult with the participant (if > 18years) and/or their parents in confidence and explain why they (or their child) cannot continue to

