participate and that they should consult with their primary care physician. We will also advise them on diet and lifestyle that they can follow to minimize the risk. If non-liver adverse findings are reported during MRI, we will provide the participant with a letter that they can show to their physician.

Phase 2&3- visit 2- Oral fructose challenge: After their initial anthropometrics and Fibroscan measurements, they will undergo an oral fructose challenge using a protocol used by Hudgins et al¹³. The participants will be provided with a drink consisting of 0.75g/kg fructose + 0.45g/kg glucose dissolved in 24 Oz of water to be consumed within 15 minutes. An average overweight adolescent of 65 kg will consume 48.75g (65 x 0.75g/kg) fructose and 29.25g (65 x 0.45g/kg) of glucose which is similar equivalent to the sugars in two soda cans²⁸.

Blood and urine will be sampled at baseline and 1 and 3 hours after fructose ingestion. During the challenge period, no other beverage (except water) or food will be allowed.

Anthropometric measurements: Height will be measured using a portable stadiometer. Body composition and weight will be measured by bioelectric impedance technology using the Tanita Dual Frequency total Body composition analyzer (Tanita Inc., Arlington Heights, IL). Measurements will be conducted in a standing position, with subjects wearing light clothing and without shoes. Height will be measured to the nearest 0.1 cm by a stadiometer situated against the wall in an upright standing position. Height and weight recorded will be used to calculate BMI as kg/m². Waist circumference (WC) will be measured using a stretch-resistance tape at the midpoint between the lower margin of the least rib and the top of the iliac crest to the nearest 0.1 inch. Waist and hip circumferences will be measured to the nearest cm in a standing position. Sitting blood pressure (systolic and diastolic blood pressure) will be measured three times using the Omron digital blood pressure monitor (HEM907XL, Omron Healthcare Inc, Lake Forest, IL). The means of these measurements will be used for analysis. Well trained personnel in the UNC NRI Human Research Core will administer questionnaires as well as measure anthropometrics, by one staff member to minimize measurement variation and margin of error.

Questionnaires: The following six sets of questionnaires will be administered to the study participants.

- Personal Interview Form: Information related to demographics

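### The baseline MRI liver-fat exclusion limit has two values: above 5% in four places, above 6% in the visit 1 instruction of section 4.2

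*Combined protocol and SAP*

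**What the plan says.** Four places set the limit at 5%:

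- Synopsis, Exclusion Criteria: "Liver fat fraction >5% as per baseline MRI scan".
- Synopsis, Safety Evaluations: further participation ends "if we find that the participant has high liver fat fraction (>5%) during our baseline MRI scan". The follow-up action is also given there: "The participant will be given a report that they can show to their physician for treatment".
- Section 3.4, Study Population, lists among the exclusions a "baseline MRI scan of liver fat fraction > 5"%.
- Section 4.2, in the paragraph on assessing liver fat and stiffness, excludes anyone above 5% from the nutrient challenge.

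One place sets it at 6%. The visit 1 paragraph of section 4.2 states "Studies have shown that 5-6% of liver fat is considered normal", with higher values said to point to raised risk. It continues: "If the MRI report of the participants shows liver fat > 6%, we will consult with the participant" or the parents, to explain why the person cannot continue to "participate and that they should consult with their primary care physician". Diet and lifestyle advice follows.

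Section 1.3 relies on this exclusion when it explains why no major risk is expected: "we will exclude individuals who are diabetic, pre-diabetic, have high liver fat at baseline".

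**The concern.** A person with baseline liver fat above 5% and up to 6% is excluded under four statements. Under the fifth, that person is described as normal and does not reach the level at which staff explain that participation must stop. The visit 1 paragraph never says outright that such a person continues; that is the implication of its wording.

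Three things are at stake.

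- **Safety.** The 5% limit sits under Safety Evaluations, and section 1.3 uses the exclusion of high liver fat to support its risk statement. Participants may be as young as 12, and the intervention is one the protocol expects to raise liver fat.
- **Follow-up of those excluded.** The synopsis gives a physician report to people excluded above 5%. Section 4.2 gives the consultation, referral and lifestyle advice above 6%. Someone excluded between the two limits would not clearly receive the latter.
- **The outcome.** MRI liver fat is the measure named in the primary objective, so this limit also fixes the permitted baseline range of the main outcome.

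**Working it through.** **Step 1: compare the statements.** The plan offers no figure to reproduce, so the check is a direct comparison.

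| Place | Limit | Consequence | Reference cited for the value |
|---|---|---|---|
| Synopsis, Exclusion Criteria | above 5% | excluded | none |
| Synopsis, Safety Evaluations | above 5% | excluded; report for physician | 10 |
| Section 3.4 | above 5% | excluded | 27 |
| Section 4.2, liver-fat assessment paragraph | above 5% | excluded from the challenge | 10 |
| Section 4.2, visit 1 | above 6%; 5-6% called normal | told they cannot continue; referral; diet advice | none |

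The two rules agree at or below 5% and above 6%. They disagree above 5% and up to 6%. Section 4.2 holds both, so it contradicts itself. No section sets an order of precedence. The conflict is in operative text and does not come from an amendment history, a redaction or the PDF conversion.

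**Step 2: consider how it would play out.** The MRI is done at visit 1, and the fructose challenge follows the next day (synopsis, Intervention; section 3.3). The visit 1 paragraph is the instruction staff would have in hand when the scan result arrives, and there is little time to settle an ambiguity.

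**Step 3: how many people could be affected.** The documents do not give the share q of people above 5% and up to 6%, so q is assumed over a range. Inputs from the plan are 48 people sent for the scan (section 3.3; section 4.2, visit 1), of whom 24 are children (synopsis, Study Design). With independent participants and the same q in both age groups:

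expected number = n × q; chance of at least one = 1 − (1 − q)^n

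| q (assumed) | Expected, n = 48 | At least one, n = 48 | Expected, n = 24 children | At least one, n = 24 |
|---|---|---|---|---|
| 1% | 0.48 | 0.383 | 0.24 | 0.214 |
| 2% | 0.96 | 0.621 | 0.48 | 0.384 |
| 5% | 2.40 | 0.915 | 1.20 | 0.708 |
| 10% | 4.80 | 0.994 | 2.40 | 0.920 |

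For example, at q = 2% and n = 48: 1 − 0.98^48 = 1 − 0.379 = 0.621.

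These are chances that someone falls in the disputed band. Wrong enrolment also requires staff to follow the visit 1 wording. The plan uses 48 both for those scanned and for those given drinks. If it means those given drinks, more than 48 may be scanned and the all-participant figures would be higher for a given q.

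**The case against.** The strongest reply is that the formal criteria govern. Both exclusion lists, the safety text and the MRI assessment paragraph say 5%. The visit 1 sentence describes whom staff will counsel and never says that anyone in the 5-6% band may enrol, so wrong enrolment would mean overlooking four explicit statements. This limits the likelihood but does not remove the conflict. The visit 1 sentence attaches 6% to being unable to continue, which is an eligibility consequence, and the plan ranks no section above another.

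Second, the safety weight is modest. No harm is shown in this band, the dose is about two sodas a day for three weeks, calorie-offset guidance is planned and a clinician is available. That stands. The defect is a stated safety limit with two values, not a demonstrated hazard.

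Third, the band share is assumed and the resulting chances run from 38% to 99%. The same q is used for children and adults, and for groups selected as genetic extremes for liver fat itself. That also stands: the figures show that an affected participant is plausible and cannot estimate how many there will be.

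Fourth, the physician report already covers people excluded above 5%. This is partly right. The private consultation, the explicit advice to see a primary care physician and the lifestyle advice remain tied to 6%.

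Finally, the documents cannot show which cut-off is clinically correct. The references behind the 5% value cannot be inspected here, and reference 10 is titled as a study in children while half the sample is adult. The case for 5% is therefore one of consistency: it is the value in the formal criteria and in four of the five places.

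**Conclusion.** The concern holds. The baseline liver-fat limit is above 5% in four places and above 6% in the visit 1 instruction, and section 4.2 contains both. This can be confirmed by reading and needs no assumption. That a person above 5% and up to 6% would continue is inferred from the visit 1 wording, which calls that range normal and gives 6% as its only trigger.

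The number affected is unknown. For assumed shares of 1% to 10%, the expectation is about 0.5 to 4.8 among 48 scanned and 0.2 to 2.4 among 24 children, given independence and a common share. The conclusion does not rest on those figures. It should be corrected because the limit is part of the trial's safety and eligibility rules, minors are included, and the correction is nearly free.

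**What to change.** Before the first scan, amend the visit 1 paragraph of section 4.2:

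1. Replace the 6% limit with above 5%, so that all five statements agree.
2. Remove the remark that 5-6% is normal as a basis for continuing.
3. Give both the physician report from Safety Evaluations and the consultation, referral and diet advice from section 4.2 to everyone excluded above 5%.

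If the sponsor has clinical grounds for preferring 6%, the other four statements would have to change instead, with a reference. Either way there should be one value.

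The cost is a wording amendment, and the threshold change itself requires no extra scans. The drawback of settling on 5% is that the few people above 5% and up to 6% whom the visit 1 wording would have kept are lost to the study.

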Study Objective(s)	
Our goal for this study is to generate preliminary data that is needed to support an application to NIH for funding of a larger, adequately-powered study to explore whether a set of genotypes, that increase the risk for nonalcoholic fatty liver disease (NAFLD), predispose individuals to increased de novo lipogenesis (DNL) and liver fat accumulation when exposed to fructose intake.
 
Primary Objective: To determine the impact of acute and prolonged exposure of fructose on hepatic lipid accumulation in adolescents and young adults (12-40 years) with high and low genetic risk for NAFLD using liver mass resonance imaging (MRI).
 
Secondary Objective: To explore the genetic-specific effects of fructose on markers of liver fat accumulation (fibroscan⁵ and fatty liver index⁶) and serum biomarkers related to lipids, uric acid and liver function.

Test Article(s) (If Applicable)	Sugar-Sweetened beverages
Study Design	
 a. We will screen 200 Caucasian children and young adults (12-40 years) to obtain 24 children and 24 young adults who are overweight/obese and drink <14 fructose drinks/week to participate in a 3-week fructose intervention study. The 200 participants will be genotyped for 10 SNPs involved in lipid metabolism and associated with increased NAFLD risk in previously published studies^{7,8}. We will select 12 children and young adults with 15 or more risk alleles and 12 children and 12 young adults with 6 or fewer risk alleles and provide them fructose + glucose⁹ drinks who will ingest one drink (equal to 2 soft drinks) per day for 3 weeks; b. We will measure liver fat using Liver MRI^{9,10} and transient elastography (Fibroscan)⁵ at week 0 and 3;

c. Data will be analyzed using paired and unpaired students T test to differentiate the responses between the time points and between the two groups, respectively.

Specific Aim2: Determine the impact of acute exposure of fructose on hepatic *de novo* lipogenesis

- Using the cohort described in Specific Aim1, we will conduct oral fructose tolerance test at week 0 and week 3;
- We will measure liver fat using Fibroscan
- Data will be analyzed using unpaired students T test and repeated measures ANOVA to differentiate the responses between and within the two groups, respectively.

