	(2) Intervention: This part is divided into two phases. Each phase entails two visits. Phase2-visit 1: The 48 enrolled (24 in each of the high and low genetic risk group) will

visit the UNC NRI clinical suite run by the Human Research Core. They will be taken to the WakeForest imaging center for their baseline MRS scan.

Visit 2: Acute fructose challenge: The next day, they will have their initial anthropometrics and Fibroscan measurements. They will then undergo an oral fructose challenge using a protocol used by Hudgins et al¹³. The participants will be provided with a drink consisting of fructose (0.75g/kg body weight) + glucose (0.45g/kg body weight) dissolved in 24 Oz of water (equal to 2 soda cans) to be consumed within 15 minutes. Blood and urine will be sampled at baseline and 1 and 3 hours after sugar drink ingestion. During the challenge period, no other beverage (except water) or food will be allowed.

3-week intervention: The 48 participants will be provided with sugar drinks for the three week period. The drinks that need to be taken per day will contain fructose (0.75g/kg body weight) + glucose (0.45g/kg body weight) dissolved in 24 Oz of water (equal to 2 soda cans) which is similar to that provided during the acute fructose challenge⁷.

[figure not shown]
Addition of glucose to fructose in the challenge and 3-week intervention induces the lipogenic effects of fructose, alleviates gastrointestinal effects of fructose and mimics the real-life situation¹⁴. They will visit at the end of each week to collect drinks for the next week. In addition, participants will be given standardized meals for the day prior to the baseline fructose challenge. They will also be instructed to avoid alcohol, juices and sodas the previous evening.

Efficacy Evaluations	Changes in liver fat accumulation through MRI scans and fibroscan measurements, and serum concentration of other lipids, liver function markers and uric acid.
Pharmacokinetic Evaluations	N/A

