- Medical History: Information related to medical conditions, procedures and surgeries
- Modifiable activity form: Information related to physical activity, sedentary time and job activities
- Medications: Information related to prescription, non-prescription and traditional medications
- Dietary data: Combination of diet recall and food frequency questionnaire will be used to obtain detailed dietary data.

Sample preparation: A total of 24 mL of blood will be drawn at fasting at baseline, 1 hour, 3 hours, at weeks 0 and 3 by a trained phlebotomist through venous puncture. After centrifugation, the serum and plasma fractions of the blood samples will be aliquoted and stored at -80°C to measure the biomarkers listed below using standard reference procedures. All samples will be labeled and inventoried as per standard protocols. Urine will be collected at the same points as blood samples collected at baseline, 3 hour at weeks 0 and 3 will be stored at -80°C. The Human Research Core will assist with phlebotomy services

Meals: All participants will be provided standardized meal for the evening prior to participation of part 1 of phase 2.

Assessment of liver fat accumulation and stiffness: Magnetic resonance imaging (MRI): We will assess liver fat accumulation at week 0 and week 3 using the 2012 Siemens MAGNETOM Skyra 3T MRI system available at the WakeForest Translational Imaging program. If the liver fat fraction >5%¹⁰ then we will exclude the participant from further participation in the nutrient challenge.

Transient elastography: We will use transient elastography to ascertain the changes in the amount of fat in the liver. Transient elastography using a **Fibroscan®** is a non-invasive method of assessing fat accumulation in liver and liver stiffness and works on the principle of vibration controlled transient elastography⁵. A vibration of mild amplitude and low frequency is transmitted through the intercostal space using a vibrator at the skin surface. The vibration induces an elastic shear that propagates through the hepatic tissue. Using pulse echo ultrasound acquisition, the velocity of the shear wave can be determined. The shear wave, directly related to tissue stiffness and expressed in kilopascal (kPa), can be a helpful aid to clinically manage patients with liver disease. The UNC Human Research Core houses a Fibroscan and its trained technicians will help with its use for this study.

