6.3 Statistical Methods

Each subject will be given sugar drink containing fructose and liver MRI scan with fibroscan measurements will be taken at baseline and end of 3 weeks. Data will be assessed using descriptive measures and confidence intervals. Paired t-tests and repeated measures regression analysis will be performed to explore the significant differences between week 0 and week 3. Also, for each subject, the area under the curve (AUC)¹³ will be computed and a linear regression with AUC as the response will be performed during the acute challenge.

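### The standardised meal and the previous-evening alcohol restriction are written for baseline only, so week 0 to week 3 changes in meal-sensitive measures compare visits with unmatched preparation

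*Combined protocol and SAP*

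**What the plan says.** Meal standardisation appears in two places.

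- Synopsis, Study Phases, (2) Intervention: "participants will be given standardized meals for the day prior to the baseline fructose challenge". The next sentence adds: "They will also be instructed to avoid alcohol, juices and sodas the previous evening".
- Section 4.2, Meals: "All participants will be provided standardized meal for the evening prior to participation of part 1 of phase 2".

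Other provisions bear on preparation at week 3.

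- Section 1.3: "We will also advise the participants to avoid fruit juices and other sodas for the duration of 3 weeks". Alcohol is not mentioned there.
- Section 4.2, Sample preparation: "blood will be drawn at fasting at baseline, 1 hour, 3 hours, at weeks 0 and 3".
- Synopsis, Specific Aim 2: "we will conduct oral fructose tolerance test at week 0 and week 3".
- Section 3.3: "They will visit again at the end of week 3 for further biomarker, MRI scan and fibroscan measurements". No preparation is given for that visit.

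Section 6.3 sets out the main comparison over time: "Paired t-tests and repeated measures regression analysis will be performed to explore the significant differences between week 0 and week 3". Section 6.1 lists FLI among the main outcome measures, while Section 2.3 treats it as a secondary marker.

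**The concern.** The investigators thought intake before the visit worth controlling at week 0, over and above the fast. If the same control is absent at week 3, the change score reflects the three weeks of drinks plus any difference in what was eaten, or drunk as alcohol, the evening before. All 48 participants receive the sugar drink, so no unexposed arm shows how large that second part is.

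Two things are at stake. A systematic difference in preparation would bias the estimated within-group change. An unsystematic one would widen the spread of the change scores, and Section 6.4 says these data will be used to size a larger study. Neither can be repaired once the week 3 samples are taken.

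**Working it through.** **1. The preparation texts side by side**

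| Element | Before week 0 | Before week 3 |
|---|---|---|
| Standardised meal | Yes: a day of meals (synopsis) or one evening meal (4.2) | Not stated |
| Alcohol avoided the previous evening | Yes (synopsis) | Not stated |
| Juice and soda avoided | Yes (synopsis) | Yes, by the 3-week advice (1.3) |
| Fasting blood | Yes (4.2) | Yes (4.2) |

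The mismatch is therefore confined to the meal and alcohol.

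**2. What the baseline provision covers**

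A day of meals and one evening meal are different procedures. Part 1 of phase 2 is not defined: it could mean the visit 1 MRI or the visit 2 challenge. The synopsis places the challenge on the day after the MRI, so meals for the day before the challenge fall on the MRI day itself. On that reading the baseline MRI was not clearly preceded by a standardised meal either. Section 4.2 labels its visits as phases 2 and 3, but its meal sentence names phase 2 alone.

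**3. Which comparisons are exposed**

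- Week 0 to week 3 change within a group: exposed, for measures sensitive to recent intake. I take these to be fasting triglycerides, FLI through its triglyceride term, and the repeated challenge. That sensitivity is a judgement, not a figure in the documents.
- 0, 1 and 3 hour values within one visit: not exposed, because they share the same preparation.
- High versus low genetic risk: write the mean change in each group as its true change plus a shift b. If b is common, (d_high + b) − (d_low + b) = d_high − d_low, so b cancels. Added variance does not.

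**4. Illustration for FLI**

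The plan gives no figure to reproduce. The equation is the one in Section 4.2; all participant values are assumed: triglycerides (TG) 100, BMI 28, GGT 25, waist 95 cm.

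L = 0.953 ln(TG) + 0.139 × BMI + 0.718 ln(GGT) + 0.053 × waist − 15.745, and FLI = 100 e^L / (1 + e^L).

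At TG 100: L = 4.389 + 3.892 + 2.311 + 5.035 − 15.745 = −0.118, so FLI = 47.1.

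| TG | L | FLI | Difference from TG 100 |
|---|---|---|---|
| 80 | −0.331 | 41.8 | −5.2 |
| 90 | −0.219 | 44.6 | −2.5 |
| 110 | −0.027 | 49.3 | +2.3 |
| 120 | 0.056 | 51.4 | +4.3 |

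**5. Illustration for the paired test**

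Let preparation shift the mean change by b standard deviations of the change, with no true effect. With two-sided alpha 0.05 (assumed), the rejection rate comes from a noncentral t distribution with n − 1 degrees of freedom and noncentrality b√n.

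| b (assumed) | n = 24 (one risk group) | n = 48 (all) |
|---|---|---|
| 0.1 | 0.076 | 0.104 |
| 0.2 | 0.156 | 0.274 |
| 0.3 | 0.291 | 0.530 |
| 0.5 | 0.650 | 0.924 |

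The documents give no value of b. The table shows only how a given shift would affect the test.

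**The case against.** A reader might infer that the whole avoidance instruction applies only to baseline and that every paired comparison is made under different conditions. The documents do not support that. Section 1.3 carries juice and soda avoidance through all three weeks, Section 4.2 requires fasting blood at both weeks, and Section 5 requires the same equipment throughout. Nothing in the documents shows that one meal or one evening changes MRI liver fat or the Fibroscan reading. On the synopsis wording, the baseline MRI may not have been standardised in the first place.

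The strongest remaining argument is that Section 2.2 makes genetic-specific effects the primary objective, and a shift common to both risk groups drops out of that contrast. This stands as far as bias is concerned. It does not protect the within-group tests that Section 6.3 plans, nor does it remove extra variance.

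It is also fair that a triglyceride shift of 10 to 20% is assumed in both size and direction; an uncontrolled evening meal could be lighter or heavier than the standard one. The FLI figures are therefore an illustration, not an estimate of bias.

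The diet questionnaires and 24-hour recalls in Section 4.2 record intake but do not equalise it. Matched fasting fixes the state on the morning of sampling but not what was consumed the evening before. Finally, this is an exploratory feasibility study that concedes limited power, which lowers the stakes. The remedy is correspondingly small.

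**Conclusion.** The point holds in a limited form. As written, the standardised meal and the previous-evening alcohol restriction apply before baseline and not before week 3, and the meal itself is described in two ways that must be reconciled. This leaves an avoidable source of bias or variance in the within-group week 0 to week 3 changes in fasting triglycerides, FLI and the repeated challenge.

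Its size is unknown. For one assumed participant, a 10 to 20% triglyceride difference moves FLI by about 2 to 5 points in either direction with no change in liver fat. The conclusion rests on reading the plan literally, and on the judgement that these measures respond to recent intake. It does not extend to MRI liver fat, to comparisons within a visit, or to bias in the high- versus low-risk contrast when the shift is common to both groups. It is a cheap improvement to make before the study runs, not a flaw that invalidates the design.

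**What to change.** Make three changes to the text.

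1. Reconcile the synopsis and Section 4.2 on whether the standardised provision is a day of meals or one evening meal.
2. Define part 1 of phase 2, so that it is clear whether the meal precedes the MRI, the challenge or both.
3. State that the same standardised meal or meals, and the same previous-evening avoidance instruction including alcohol, apply before the week 3 assessment as before baseline.

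The cost is one more meal, or one more day of meals if the synopsis version is kept, for each of the 48 participants, and a sentence or two of protocol text. No visit, staff or procedure is added.
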